6.6 Examination of Subgroups

Subset analysis for the following subgroups will be performed for the primary and secondary efficacy endpoints:

- Age group (6 – 11 years vs. 12 - 17 years vs. ≥ 18 years),
- Gender (male vs. female),
- Race (White vs. Black or African American vs. Asian vs. other),
- Ethnicity (Hispanic vs. Non-Hispanic),
- Randomized vIGA-AD score (mild (2) vs. moderate (3)),

	STATISTICAL ANALYSIS PLAN, Version 3.0
Protocol Number: ARQ-151-311	Sponsor: Arcutis Biotherapeutics, Inc.

- Actual baseline vIGA-AD score (mild (2) vs. moderate (3)),
- Baseline % BSA (<10% vs. $\geq 10\%$),
- %BSA categories based on tertiles,
- Baseline EASI total score (≤ 7 vs > 7),
- Baseline EASI total score based on tertiles
- Fitzpatrick skin type at Screening (Type I, II and III vs. Type IV, V, and VI),
- Prior inadequate response, intolerance, or contraindication to Topical Corticosteroids (yes vs. no),
- Facial Involvement (yes vs. no)

For subgroup based on tertiles, tertiles will be derived using pooled data from both treatment group based on the ITT population.

Details on these analyses are described in Section [12.4](#).

7 STUDY SUBJECTS

7.1 Disposition of Subjects

All subjects who provide informed consent will be accounted for in this study. The number of subjects who were screened and who failed screening (screen failures) will be presented. The reasons for screen failure will be presented for all screened subjects who failed screening.

The number of subjects randomized will be presented by treatment group. The number and percentage of the subjects included in each analysis population will be provided by treatment group. The number and percentage of the subjects who completed the study, who discontinued the study, the reasons for study discontinuation, and early termination due to COVID-19 disruption will be presented by treatment group. The percentages will be calculated using the number of the randomized subjects as denominator.

Number of days in the study will be summarized with descriptive statistics by treatment group and overall. For each subject, the number of days in the study will be calculated as following:

$$\text{Number of days in study} = \text{Date of completion/discontinuation} - \text{1}^{\text{st}} \text{ dose date}^* + 1$$

	STATISTICAL ANALYSIS PLAN, Version 3.0
Protocol Number: ARQ-151-311	Sponsor: Arcutis Biotherapeutics, Inc.

* For randomized subjects who discontinued study before the first application of study treatment, the date of randomization will be considered instead of the date of the first application of study treatment.

A listing of subject's disposition and randomization will be provided. Information on first screening for subjects who were rescreened, including the rescreened subject identifier and the reason for first screening failure, will be presented under the first screening subject identifier. The reason for screening failure will be listed as well.

A table of randomized strata vs. actual strata will be provided if there is any mis-randomization discrepancy.

7.2 Protocol Deviations

A data review will be conducted before database lock by the Medical Monitor and the Sponsor to classify protocol deviations as minor or major.

The number and percentage of subjects with at least one important protocol deviation (including important protocol deviations associated with COVID-19) will be summarized by deviation category and treatment group using the safety analysis set.

A listing of all protocol deviations will also be provided. The protocol deviations associated with COVID-19 and major PDs will be flagged.

8 DEMOGRAPHIC AND OTHER BASELINE CHARACTERISTICS

Demographics and baseline characteristics will be summarized with descriptive statistics using the ITT and safety population. The list of demographics and baseline characteristics to be summarized will include:

- Age (years)
- Age Group: 6-11, 12-17, 18-64 and ≥ 65
- Childbearing potential
- Sex at birth
- Ethnicity
- Race*
- Baseline Height (cm)

	STATISTICAL ANALYSIS PLAN, Version 3.0
Protocol Number: ARQ-151-311	Sponsor: Arcutis Biotherapeutics, Inc.

- Baseline Weight (kg)
- Baseline Body Mass Index (BMI) (kg/m²): Adult, Child/Adolescent
- Fitzpatrick Skin Type
- Prior failure of Topical Corticosteroids, Topical Calcineurin Inhibitors, Eucrisa
- Atopic Dermatitis involvement on the face, on the eyelids
- Baseline vIGA-AD
- Average weekly baseline WI-NRS
- Daily baseline WI-NRS
- Baseline BSA (%)
- Baseline BSA (%) Group - <10% and ≥10%, tertile groups
- Baseline EASI total score
- Baseline EASI score group - ≤7 and >7, tertile groups
- Baseline SCORAD
- Baseline DLQI/CDLQI
- Baseline DFI
- Baseline POEM
- Baseline PHQ-8
- Baseline PHQ-A
- Baseline CDI-2

*Subjects who reported more than one race will be summarized as 'Multiple' races in the table. All races selected will be displayed in the listing.

Adult: BMI (kg/m²) = (weight in kg)/ [(height in cm/100)²]. Baseline height will be used to derive BMI for each visit since height is not collected at all visits.

Child and Adolescent (6 to 17 years): After BMI is calculated using the same formula above for children and teens, it is expressed as a percentile obtained from either a graph or a percentile calculator. Percentiles will be calculated using data files and instructions provided by the CDC (https://www.cdc.gov/growthcharts/percentile_data_files.htm). Baseline height will be used to derive BMI for each visit since height is not collected at all visits.

	STATISTICAL ANALYSIS PLAN, Version 3.0
Protocol Number: ARQ-151-311	Sponsor: Arcutis Biotherapeutics, Inc.

A listing of all demographics, analysis population flag, reason not included in the efficacy analysis will be provided.

9 SURGICAL AND MEDICAL HISTORY

Surgical and medical history will be coded according to the Medical Dictionary for Regulatory Activities (MedDRA), Version 25.0.

Surgical and medical history will be summarized by system organ class (SOC) and preferred term (PT) using the safety analysis set. A subject who experienced the same surgical and medical history event multiple times will be counted only once for the corresponding PT. Similarly, if a subject experienced multiple surgical and medical history events within the same SOC, the subject will be counted only once for that SOC. Surgical and medical history events will be sorted alphabetically by SOC and within each SOC the PT will be presented by descending frequency in the safety analysis set.

10 PRIOR AND CONCOMITANT MEDICATIONS

Medications will be coded according to the World Health Organization Drug Dictionary (WHO-DD) B3 September 2022.

Prior medications are defined as any medication started and discontinued prior to the first study treatment dosing. Concomitant medications are defined as any medication taken after the first study treatment dosing, including those who started prior to the first study treatment date and continued past that date. See [Appendix 2](#) for handling of completely or partially missing dates for prior and concomitant medications.

Incidence of prior and concomitant medications will be tabulated by ATC level 3 and PT using the safety analysis set. A subject with the same medication taken multiple times will be counted only once for the corresponding PT. Similarly, if a subject has taken more than one medication within the same ATC level, then the subject will be counted only once for that ATC. Prior and concomitant medications will be sorted alphabetically by ATC level and within each ATC level, the PT will be presented by descending order.

	STATISTICAL ANALYSIS PLAN, Version 3.0
Protocol Number: ARQ-151-311	Sponsor: Arcutis Biotherapeutics, Inc.

11 STUDY TREATMENT EXPOSURE AND TREATMENT COMPLIANCE

A summary of exposure related to Roflumilast cream and the vehicle will be presented using the safety population by treatment group. It will include descriptive statistics on the number of days on IP, as well as the number of investigational product applications based on diary, for each treatment group. The number of days on IP, will be calculated as follows:

$$[(\text{last treatment date} - \text{first treatment date}) + 1].$$

For each subject, investigational product application compliance (%) will be calculated as follows:

$$\frac{\text{Number of investigational product applications}}{\text{Number of expected investigational product applications}} \times 100$$

Number of investigational product applications will be calculated as number of expected investigational product applications minus number of doses missed. Number of doses missed and the date that the dose was missed were collected in eCRF.

Number of expected investigational product applications will be calculated as calculated as last treatment/interruption date – first treatment date + 1. If latest treatment date \geq latest interruption date, then the latest treatment date will be used; otherwise, latest interruption date will be used in deriving the expected number of IP applications.

Descriptive statistics for the compliance as well as the number of missed applications, subjects with < 80%, [80% - 100%], and >100% compliance will be presented by treatment. Furthermore, the incidence of subjects who missed more than 3 consecutive doses and compliant subjects will be presented by treatment.

A subject will be considered compliant with the dosing regimen if the subject meets both of the following requirements:

- applies at least 80% of the expected applications during the study drug application period
- does not miss more than 3 consecutive doses

Total weight of study medication applied (determined by weighing the study medication before and after use) will be summarized by treatment using descriptive statistics. Weight of study medication used will be documented in source documents and in eCRF. Total weight of IP used is determined by subtracting minimum of (returned, remained) tube weight from the maximum of

	STATISTICAL ANALYSIS PLAN, Version 3.0
Protocol Number: ARQ-151-311	Sponsor: Arcutis Biotherapeutics, Inc.

(dispensed, prepared) tube weight for each tube that was dispensed and summing the weights. Calculate Actual IP Used: maximum of (dispensed, prepared) tube weight minus minimum of (returned, remained) tube weight = ____ grams

If a tube is not returned at the end of the study or a tube weight is missing, actual IP used for the tube and total weight of IP applied during study will be missing.

Number of days on IP and compliance, including compliance collected at each clinic visit, will be displayed in a listing of study treatment administration by subject, for each treatment. A listing of drug accountability including the kit number, tube number, dispensed and returned weight will also be provided.

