3.3 Treatment

Roflumilast cream 0.15% or vehicle cream will be administered QD for 28 days (+/- 3 days).

- Roflumilast cream 0.15%
- Vehicle cream

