4.3 Per Protocol (PP) Population

Per protocol population will include all subjects who are randomized, at least 80% compliant with study medication application, have a vIGA-AD assessment within the Week 4 visit window and show no “major deviations” from the study protocol that would affect the interpretation of efficacy. A complete list of major deviations from the study protocol will be created prior to unblinding and include a list of all subjects who will be excluded due to those major deviations. See section [7.2](#) for more details.

All subjects will be analyzed according to the actual treatment group they received and the stratum they belong to. Actual and randomized treatment will only differ if the subject received the wrong treatment throughout their participation in the study.

4.4 vIGA-AD Moderate ITT Population

vIGA-AD Moderate ITT population will be a subset of the ITT population with vIGA-AD score (randomized score) ‘Moderate’ at randomization.

All subjects will be analyzed according to the treatment group and the stratum to which they were randomized.

4.5 vIGA-AD Moderate PP Population

vIGA-AD Moderate PP population will be a subset of the PP population with vIGA-AD score (actual score) ‘Moderate’ at randomization.

	STATISTICAL ANALYSIS PLAN, Version 3.0
Protocol Number: ARQ-151-311	Sponsor: Arcutis Biotherapeutics, Inc.

All subjects will be analyzed according to the actual treatment group they received and the stratum they belong to. Actual and randomized treatment will only differ if the subject received the wrong treatment throughout their participation in the study.

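### SAP compliance ends at the subject's own last treatment or interruption date, so an early stopper with few or no logged misses can pass the 80% per-protocol criterion (minor)

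*SAP*

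**What the plan says.** SAP section 11 (Study Treatment Exposure and Treatment Compliance) defines compliance as applications divided by expected applications. On the denominator it says: "Number of expected investigational product applications will be calculated as calculated as last treatment/interruption date", minus the first treatment date, plus one. If the latest treatment date is on or after the latest interruption date, the treatment date is used; "otherwise, latest interruption date will be used in deriving the expected number of IP applications". The numerator is "calculated as number of expected investigational product applications minus number of doses missed", with missed doses and their dates taken from the eCRF. No planned end of treatment enters the formula, and nothing says whether doses after a permanent stop are expected or missed. Protocol section 6.5 does not define the end of the expected period either.

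SAP section 3.3 gives the planned regimen: cream "will be administered QD for 28 days (+/- 3 days").

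SAP section 4.3 admits a randomized subject to the PP population if the subject is "at least 80% compliant with study medication application", is found to "have a vIGA-AD assessment within the Week 4 visit window", and has no major deviation affecting interpretation of efficacy. The vIGA-AD Moderate PP population (4.5) is a subset of this. Section 11 adds a second condition for calling a subject compliant, that the subject "does not miss more than 3 consecutive doses", but section 4.3 does not repeat it. The section 11 table has three compliance bands: below 80%, then "80% - 100%], and >100% compliance will be presented by treatment".

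**The concern.** A PP analysis is meant to show the effect in subjects who followed the regimen. Here the adherence test is relative to however long the subject chose to treat. A subject who stops after ten days and logged no misses looks fully adherent.

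The second problem is that the score is not determined by what the subject did. Whether a stop is recorded as a last treatment date, as an interruption carried forward, or as a run of missed doses changes the answer, and the SAP does not say which applies.

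The observed-data PP analysis is a listed sensitivity analysis for the primary endpoint (12.1.3), and the Moderate PP analysis is one for the Moderate secondary endpoint (12.2). At stake is whether those analyses describe adherent subjects, and whether the compliance table can overstate adherence.

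**Working it through.** The documents give no numerical result for this point, so there is none to reproduce. The check applies the section 11 formula directly.

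**Inputs.** First treatment on Day 1. E = the later of last treatment day and latest interruption day (SAP 11). M = logged misses (SAP 11). Planned applications = 28 (SAP 3.3). PP threshold = 80% (SAP 4.3).

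**Formula.** Compliance = (E − M)/E × 100. With M = 0 this is 100% for every E. Because M cannot be negative, it never exceeds 100%, so the band above 100% is always empty.

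**Early stop, no later interruption date**

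| Last dose | Logged misses | SAP compliance | Share of 28 planned |
|---|---|---|---|
| Day 7 | 0 | 7/7 = 100% | 7/28 = 25.0% |
| Day 10 | 0 | 10/10 = 100% | 10/28 = 35.7% |
| Day 14 | 0 | 14/14 = 100% | 14/28 = 50.0% |
| Day 20 | 0 | 20/20 = 100% | 20/28 = 71.4% |
| Day 10 | 2 | 8/10 = 80.0%, passes | 8/28 = 28.6% |
| Day 10 | 3 | 7/10 = 70.0%, fails | 7/28 = 25.0% |
| Day 14 | 2 | 12/14 = 85.7%, passes | 12/28 = 42.9% |

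So the condition of few or no logged misses is essential: three misses are enough to fail a Day 10 stopper.

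**Same behaviour, different records.** Ten doses applied, last dose Day 10:

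| E | M | Compliance | 80% test |
|---|---|---|---|
| 10 | 0 | 100% | pass |
| 11 | 1 | 10/11 = 90.9% | pass |
| 12 | 2 | 10/12 = 83.3% | pass |
| 13 | 3 | 10/13 = 76.9% | fail |
| 28 | 18 | 10/28 = 35.7% | fail |
| 10 | 18 | (10 − 18)/10 = −80% | fail |

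The last row arises if doses after the stop are logged as missed while the denominator stays at the last dose. The limb on consecutive misses would catch the stopper only if days after stopping are logged as missed, and PP does not invoke it.

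**Who remains after the other PP requirements**

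- *Week 4 vIGA-AD.* The schedule (SAP 3.2) gives Day 29 ± 3, that is Day 26 to 32; SAP Table 2 gives Day 23 to 43. Section 4.3 does not say which it means. Under either, an early-termination visit soon after a Day 7, 10 or 14 stop does not qualify. Those subjects are exposed only if they stay in the study off treatment. A later stop with an early-termination visit from Day 23 could qualify under Table 2.
- *Staying in the study.* Protocol 4.8.6 (stopping treatment) is separate from 4.8.7 (leaving the study), and SAP 13.1 lists the two kinds of discontinuation separately.
- *Reason for stopping.* Adverse-event and lack-of-efficacy discontinuers are set to missing in observed-case analyses (SAP 5.5). For other reasons, SAP 12.1.1 applies treatment policy, so their values stay in.
- *Deviation list.* SAP 4.3 requires a list of major deviations, and of the subjects excluded for them, before unblinding; 7.2 describes the review. Neither names a rule on early stopping.

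**With a planned-period denominator.** No cream is applied in clinic at the Day 29 visit (SAP 3.2), so for a Week 4 visit on Day V the period ends at the earlier of Day 28 and V − 1. Fewest applications that reach 80%, and the result one below:

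| V | E | First pass | One fewer |
|---|---|---|---|
| 26 | 25 | 20/25 = 80.0% | 19/25 = 76.0% |
| 27 | 26 | 21/26 = 80.8% | 20/26 = 76.9% |
| 28 | 27 | 22/27 = 81.5% | 21/27 = 77.8% |
| 29 or later | 28 | 23/28 = 82.1% | 22/28 = 78.6% |

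The Day 10 stopper then scores 10/25 = 40.0% at best and fails for every visit from Day 26 to 32.

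**The case against.** The strongest reply is that the exposed group is narrow and that other steps already guard it. Much of this stands.

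- The deviation step in 4.3 is a subject-level exclusion made before unblinding, inside the PP definition. It could remove a Day 10 stopper. What it lacks is a stated rule, so removal rests on judgement.
- A reader might infer that adverse-event and lack-of-efficacy stoppers contaminate the PP result. The documents do not support that. Although 5.5 speaks of leaving the study, the advice quoted in SAP section 1, the example in 12.1.1 and the wording in 6.2.3 all concern stopping treatment, so the likely intent is that these subjects do not contribute.
- Diaries record missed doses (Protocol 4.8.5), and compliance determination is referred to an IP Handling Manual that is not available here. Sites may log doses after a stop as missed. The SAP does not require it, and logging them without moving the denominator gives the negative value above.
- Adherence while treated is a legitimate quantity, and Protocol 6.5 permits a subject-specific denominator. SAP 11 also reports days on IP and number of applications, so short exposure stays visible. That answers most of the criticism of the table, but neither quantity affects PP membership.
- Counting every unapplied dose as missed would also catch interruptions that Protocol 5.9 permits. Seven doses give 21/28 = 75%. The present formula gives the same 75% if those doses are logged, so the question already exists and needs an explicit answer.

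**Conclusion.** The point holds as a minor one. As written, the 80% criterion does not reliably exclude subjects who stopped early, and the same stop can pass or fail according to how it is recorded. The subjects affected must meet four conditions together: they stopped early for a reason other than an adverse event or lack of efficacy, have few or no logged misses, have a vIGA-AD in the Week 4 window, and are not removed by the deviation list. The documents give no rate for this group, so no count can be derived; it is probably small.

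A reader might infer that the trial's main conclusion is at risk, or that the PP set will contain many early stoppers. Neither follows. Only the supportive PP and vIGA-AD Moderate PP analyses and the compliance table are affected; the ITT analysis and the alpha plan are not.

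Two limits apply. The protocol supplied is the Original version, whereas the SAP follows Amendment 4. The IP Handling Manual could also settle how doses after a stop are logged.

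**What to change.** In the SAP, before unblinding:

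1. For the PP criterion, set expected applications from Day 1 to the earlier of Day 28 and the day before the Week 4 visit attended in its window. Use Day 28 if none was attended. An early-termination visit does not shorten the period. If dosing continued past Day 28, end the period at the last dose before the Week 4 visit.
2. Count unapplied doses in that period as missed, including those after permanent stopping, and state explicitly how protocol-permitted interruptions are counted.
3. State which Week 4 window, Day 26 to 32 or Day 23 to 43, the PP definition uses.
4. In the compliance table, report the planned-period figure beside the present ratio, label the latter 'compliance while on treatment', and drop the band above 100%.

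The cost is SAP wording and one derivation. PP may lose a few subjects and reported compliance may fall slightly.

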12 EFFICACY ANALYSIS

12.1 Primary Efficacy Endpoint Analysis

12.1.1 Primary Efficacy Endpoint and Estimand

The vIGA-AD is a static evaluation of qualitative overall AD severity. This global assessment scale is an ordinal scale with five severity grades (reported only in integers of 0 to 4). Each grade is defined by a distinct and clinically relevant morphologic description that minimizes inter-observer variability. vIGA-AD is evaluated for the entire body except the scalp, palms, and soles.

The primary efficacy endpoint is vIGA-AD success, defined as an vIGA-AD score of ‘clear’ (0) or ‘almost clear’ (1) plus at least a 2-grade improvement from Baseline at Week 4.

The primary estimand is described by the following attributes:

Population: Patients with Atopic Dermatitis

Endpoint: vIGA-AD success at Week 4

Intercurrent events: In the course of the 4-week randomized treatment period, subjects may be exposed to possible known or unknown intercurrent events that could possibly impact the estimates of the estimand, such as treatment discontinuation due to a specific adverse effect or perhaps a lack of effect. A composite strategy will be implemented that handles subjects who discontinue due to lack of efficacy or adverse event as missing not at random differently than all other subjects. That is, subjects who discontinue due to lack of efficacy or adverse event will be treated as non-responders for all pre-specified analysis visits (refer to Section 5.4) for which the subject’s last dose day falls within the analysis window or is prior to the start of the analysis window (refer to

	STATISTICAL ANALYSIS PLAN, Version 3.0
Protocol Number: ARQ-151-311	Sponsor: Arcutis Biotherapeutics, Inc.

Section 5.5) while the “Treatment Policy Strategy” will be adopted for handling intercurrent events in this study other than discontinuation due to lack of efficacy or adverse event.

Population-level summary: ratio of the odds of achieving vIGA-AD success after 4 weeks of using roflumilast cream 0.15%, relative to the odds of success after 4 weeks using a matching vehicle cream in the ITT population.

The supportive population-level summary: the proportion difference between Roflumilast cream 0.15% and vehicle groups will be provided for the patients who achieve vIGA-AD success at week 4 in the ITT population.

